2.1.2. Exclusion criteria

We will have minimal exclusion criteria. Patients will be excluded if they do not speak English or are unable to understand the consents as exhibited by failing the mini quiz. Patients will also be excluded if they have a severe speech impediment of any kind since they need to be able to converse with a mentor or mentee over the telephone. Patients over the age of 75 will also be excluded since it is unclear if they will derive the same benefit from getting their HbA1c in control.

2.2. List all screening and/or eligibility requirements.

We will electronically create a list of CMCVAMC patients with at least two diagnosis codes for diabetes (ICD-10 code 250) and least two laboratory tests in for an HbA1c. We will exclude people if their current age is \leq 30 and $>$ 75 years of age. We will then review the list and determine who qualifies as a potential mentee and a potential mentor. Letters will be sent to potential participants letting them know that they may be eligible for a study with a brief description of the study and give them a number if they would like to learn more or to request no further contact. We will also notify potential participants that if we do not hear from them we will give them a call in the following weeks.

Potential mentors will be identified and contacted in a similar manner.

2.3. Explain any special test or evaluations potential subjects may have to undergo before they are actually determined to be eligible for the study.

When patients are contacted over the phone we will give them an additional description of the study and for those interested we will ask them at what age they developed diabetes. Those who indicate they developed diabetes before the age of 30 will be excluded from participating. The same will be true for when we contact potential mentors. We will also ask them about how comfortable they are with speaking English. Those who indicate discomfort with speaking English or are unintelligible over the phone will also be excluded from participating.

2.4. Not Applicable; subjects not recruited; chart review.

3. If applicable, indicate what populations will be targeted for recruitment as participants. Check all that apply.

Males	
Females	
Inpatients	
Outpatients	
VA Employees	
Non-English Speaking**	
Veteran Family members***	
Non-Veterans***	
Other (Specify)	
Not Applicable, chart review	

3.1. **For non-English speaking subjects - If an investigator proposes to use a participant population that does not speak or read English, a copy of the translated document, as

well as the English version, needs to be forwarded to the IRB for approval. Translator certification is also required.

- 3.2. ***If non-veterans will be recruited for this study, explain why sufficient veterans are not available to participate in the project [VHA Handbook 1200.5, paragraph 16a]. Veteran's spouses/partners, caregivers, etc. are considered non-veterans for the purposes of this study.
- 3.3. ***Has approval to recruit non-veterans been received from the ACOS/R&D and Medical Center Director?
 - 3.3.1. Not Applicable
 - 3.3.2. Pending (*Non-veteran forms should be used. IRB office will obtain approval from ACOS/R&D and Medical Center Director.*)

- 4. **Does this project target a specific race or ethnic group as participants?** YES NO
If yes, check all that apply.

Race	
American Indian or Alaskan Native	
Asian	
Black or African American	
Native Hawaiian or other Pacific Islander	
Black, not of Hispanic origin	
White, not of Hispanic origin	
Other	

Ethnicity	
Hispanic or Latino	
Not Hispanic or Latino	
Other	

- 4.1. Provide justification why this/these group(s) was/were chosen.

- 5. **What is the age range of participants?** Check all that apply.

Children (Under 18) Requires Waiver from CRADO (VHA Directive 2001-028, Research Involving Children)	
Young Adults (18-21)	
Adults (22-65)	
Seniors (Over 65)	
Over 89	
Not Applicable, chart review	

- 6. **Are there specific reasons why certain populations (i.e., age, gender or ethnic groups) are excluded as participants?** YES NO N/A

- 6.1. If yes, specify reasons. We excluded people in the age groups younger than 30 years and older than 75 years of age. Patients under the age of 30 were excluded to ensure we are identifying a population with type 2 diabetes, and patients over the age of 75 will also be excluded since it is unclear if they will derive the same benefit from getting their HbA1c in control.

- 7. **Does the project require enrollment of the following classes of participants?**

	YES	NO
a. Employees		
b. Individuals with impaired decision making capability		
c. Pregnant women		
d. Economically and/or educationally disadvantaged persons		
e. Prisoners		
f. Illiterate, limited, or no English language proficiency		
g. Terminally ill patients		

While the study does not require the enrollment of these groups we anticipate that we will enroll economically and/or educationally disadvantaged people as well as people who may have limited health literacy. All study materials including consent forms will be read to participants. Only those who fail the mini-quiz and thus seem not to comprehend the consent process will be excluded.

- 7.1. If applicable, what is the justification for including any of the above classes of participants in the project?
- 7.2. If the project requires enrolling any of the above classes of participants describe any project-specific measures or special considerations, steps, or safeguards to ensure that these individuals are adequately protected.

8. Describe the exact plan how subjects will be identified and recruited for the study.

- 8.1. Discuss methods, e.g., referrals from physician offices, clinics, programs, or through advertisements and brochures.

We will electronically create a list of CMCVAMC patients with at least two diagnosis codes for diabetes (ICD-9 code 250 and ICD 10 codes starting with E11) and at least two laboratory tests in for an HbA1c. We will exclude people if their current age is ≤ 30 and > 75 years of age. We will then review the list and determine who qualifies as a potential mentee and a potential mentor based on past HbA1c values. This will be an ongoing process.

Letters will be sent to potential participants letting them know that they may be eligible for a study with a brief description of the study and give them a number of the project manager who they can call if they would like to learn more or to request no further contact. We will also notify potential participants that if we do not hear from them we will give them a call in the following weeks. Potential mentors will be identified and contacted in a similar manner.

When patients are contacted over the phone we will give them additional description of the study and for those interested we will ask them at what age they developed diabetes. Those who indicate they developed diabetes before the age of 30 will be excluded from participating. The same will be true for when we contact potential mentors. We will also ask them about how comfortable they are with speaking English. Those who indicate discomfort with speaking English or are unintelligible over the phone will also be excluded from participating.

Those interested in participating in the study will be invited into the CMC VAMC for a face to face meeting with the study team. At that time if still interested participants and mentors will complete the consent process in person including completing a mini-quiz about the process. Those who fail the mini-quiz will be excluded from the study at that time; however, they will be reimbursed the \$50 for coming in for an in person visit. We anticipate almost everyone who comes in for a face to face visit will be entered into the study.

9.
 - 9.1. If using a clinic, be specific about who will identify the potential subject and how that information will be transmitted to the research staff.
 - 9.2. If snowball method will be used, discuss the process and how the first individuals will be recruited.
 - 9.3. Describe how information will be disseminated to subjects, e.g. handouts, brochures, flyers and advertisements (include all recruitment materials with this submission).

10. Informed Consent

- 10.1. Informed Consent will not be sought.
- 10.2. Written informed consent from participants (VA Form 10-1086 is attached). **X**

- 10.3. Written informed consent from participants' legally authorized representative (LAR) as required by VA policy and/or applicable state laws (VA Form 10-1086 is attached).
- 10.4. Request Waiver of Documentation of Informed Consent
- 10.5. List the **title** of the key personnel involved in the following activities:
 - 10.5.1. **Person Obtaining Consent**
 - 10.5.1.1. Provide the title(s) of individual(s) Program Specialist
 - 10.5.1.2. Type of training received to perform this process CPRS training, CITI training, HIPPA training, and scanner training.
 - 10.5.2. **Pre-Recruitment Screening** (the use of medical records and other data bases to determine populations and individuals eligible for the study), **Data Base Programmer and Project Manager or Program Specialist**
 - 10.5.3. **Recruitment Process** (the process in which individuals are contacted and first introduced to the study and to the possibility of participating as subjects), **Project Manager or Program Specialist**
 - 10.5.4. **Informed Consent Process** (the process by which recruited subjects are fully informed about participating in the study and then formally give their voluntary consent for participating), **Project Manager or Program Specialist**
 - 10.5.5. **Screening of Recruited Subjects** (those activities in the protocol in which a final determination of eligibility of prospective subjects is made during the early phases of the study, using laboratory data, inclusion and exclusion criteria, and other person-specific information), **Project Manager or Program Specialist**
 - 10.5.6. Include the breakdown of each individual's responsibilities:
 - 10.5.6.1. Principal Investigator, **[name], M.D. will be responsible for the oversight of this entire study**
 - 10.5.6.2. Co-Principal Investigator, N/A
 - 10.5.6.3. The Project Manager [name] or Research Coordinator, [name] or other IRB approved research staff will be responsible for the IRB administration, screening, the recruitment and consent, data collection including measuring BMI, blood pressure, and interviews (over the phone and in-person). They will also be responsible for training the mentors and mentee-mentor coordination.
 - 10.5.6.4. Additional research staff by title, **The Project Manager [name] or Research Coordinator, [name] will be responsible for IRB administration.**
- 10.6. Will informed consent be obtained from potential subjects prior to determining eligibility?
 YES NO N/A
- 10.6.1. If no, provide justification and a HIPAA Waiver of Individual Authorization for Disclosure of Protected Health Information.

To make the recruitment process efficient we will need to screen for patients with diabetes, in the correct age range, with the lab results as described above. Please see the attached HIPAA Waiver of Individual Authorization for Disclosure of Protected Health Information for approval of this activity.
- 10.7. Define when a subject is enrolled into the study, e.g. after the subject signs the informed consent or after randomized to treatment.

After the informed consent is complete the patient will be enrolled in the study.
- 10.8. Describe:

- 10.8.1. The process when informed consent will be obtained and protecting patients' privacy.

Informed consent will be obtained at the CMC VA Medical Center in a semi-private room with cubicles. This room usually has only one person working in it at a time and thus affords audio privacy. All study materials including informed consent forms will be read to the participant.

- 10.8.2. Any waiting period between informing the prospective participant and obtaining consent. **No**
10.8.3. Steps taken to minimize the possibility of coercion or undue influence.

The consent process will explain how participation is voluntary and will not affect the care or services the patient is eligible from the Philadelphia VA Medical System. Participants will be told they can withdraw from the study at any time. Participants will only receive a reimbursement to defray the costs of travel and cover the participant's time.

- 10.9. Provide the language

- 10.9.1. used by those obtaining consent Please see attached script.
10.9.2. understood by the prospective participant or the legally authorized representative Please see attached script.

- 10.10. Provide location where informed consent will be obtained. **The CMC VA Medical Center**

11. **Waiver or Alteration of Informed Consent Requirements/Waiver of Requirement to Obtain Documentation of Informed Consent**

- 11.1. Are you requesting a waiver or alteration of informed consent? (*Check all that apply*)

11.1.1. No

11.1.2. Yes; provide justification.

11.1.3. Yes; for recruitment purposes only.

11.1.3.1. An IRB may approve a consent procedure which **does not include, or which alters**, some or all of the elements of informed consent set forth in this section, or waive the requirements to obtain informed consent provided the IRB finds and documents that:

- 1. The research involves no more than minimal risk to the subjects;
- 2. The waiver or alteration will not adversely affect the rights and welfare of the subjects;
- 3. The research could not practicably be carried out without the waiver or alteration; and
- 4. Whenever appropriate, the subjects will be provided with additional pertinent information after participation
- 5. The research or demonstration project is to be conducted by or subject to the approval of state or local government officials and is designed to study, evaluate, or otherwise examine:
 - a. Public benefit or service programs;
 - b. Procedures for obtaining benefits or services under those programs;
 - c. Possible changes in or alternatives to those programs or procedures; or

- d. Possible changes in methods or levels of payment for benefits or services under those programs.

11.2. **Are you requesting a waiver to obtain documentation of informed consent?**

11.2.1. No **X**

11.2.2. Yes; provide justification.

11.2.2.1. An IRB may **waive the requirement for the investigator to obtain a signed consent** form for some or all subjects if it finds either:

- 1. That the only record linking the subject and the research would be the consent document and the principal risk would be potential harm resulting from a breach of confidentiality. Each subject will be asked whether the subject wants documentation linking the subject with the research, and the subject's wishes will govern; or
- 2. That the research presents no more than minimal risk of harm to subjects and involves no procedures for which written consent is normally required outside of the research context.
- **NOTE: In cases in which the documentation requirement is waived, the IRB may require the investigator to provide subjects with a written statement regarding the research.**

Q. **Compensation** (The amount of compensation may not constitute an undue inducement to participate in the research.)

1. Summarize any financial compensation that will be offered to subjects.

All participants will receive \$50 for each in person visit. Mentors will also receive an additional \$20 per month if they call their mentee 4 times per week. Mentors and mentees will receive an additional \$40 for each qualitative interview completed.

2. Provide the schedule for compensation. **Baseline, 6 months, 12 months, and for arm 2 and 4 18 months.**
- 2.1. Per study visit or session. \$50
- 2.2. Total amount for entire participation. **Arm 1 \$150, Arm 2 up to \$460, Arm 3 up to \$270, Arm 4 up to \$320.**
3. Explain how compensation will be provided via cash, voucher, gift card, etc. **Participants will be given vouchers which they can then redeem for cash from the CMC VA cashier.**
4. If financial compensation will be prorated, explain the process. **N/A**
5. Not Applicable -

R. **Withdrawal/Early Withdrawal**

1. Describe how and when a subject may withdrawal from the study. **Subjects may withdraw at any time. Any request may either be expressed verbally or in writing.**
2. Provide procedures for the orderly termination of participation by the participant and if any consequences would result from early withdrawal from the study.

There will be no consequence of early withdrawal. After submitting a request to withdraw or written or verbally the study participation will be terminated. If a mentor withdraws before 4 months, his or her mentee will be re-matched to another mentor.

3. Explain if survival data is required. If so, clarify how data will be obtained. **N/A**
4. Not Applicable; subjects not recruited; chart review.

S. Risk/Benefit Assessment

1. Potential Study Risks

- 1.1. Describe and assess all of the following risks that may be associated with the research:
 - 1.1.1. Physical **Minimal**
 - 1.1.2. Psychological **Minimal**
 - 1.1.3. Social **Minimal**
 - 1.1.4. Economic **Minimal**
 - 1.1.5. Monetary **Minimal**
 - 1.1.6. Legal **Minimal**
 - 1.1.7. Loss of confidentiality **Minimal**
 - 1.1.8. Assess the likelihood and seriousness of such risks. **Minimal**
 - 1.1.9. Other
- 1.2. Specify what steps will be taken to minimize these risks.

Patients will need to complete a mini-quiz after completing the informed consent to assure the researchers they understand the consent procedure. Those who fail the mini-quiz will be given \$50 for the in person visit but not enrolled in the study. All participants will be notified that participation is voluntary and they can terminate participation at any time. They will also be notified that their care will not be affected by their participation.

The greatest risk to patients will be loss of confidentiality. Mentors and mentees will be informed that their conversations are confidential and should not be shared. Mentees will need to provide a working phone number which will be provided to the mentor. Mentees will be informed of this process up-front.

Tracking data with identifiable information will be kept in a different data base than the analytic data base. All databases will be password protected and reside on VA servers. Neither data base will be removed from the VA server and will be behind VA firewalls. Paper files will be kept in locked filing cabinets and will not leave the CMC VAMC or Annex. Papers will be kept in locked files when not being actively used. All participants will be given a study ID number and this will be the only link between the analytic files and the tracking data base.

- 1.3. If methods of research create potential risks, describe other methods, if any, that were considered and why they will not be used. **N/A**
- 1.4. If chart review, breach of confidentiality is always a concern. Specify what steps will be taken to minimize these risks.

Charts will be reviewed to determine if a potential subject may be eligible for the study. Only IRB approved study personnel will access charts from VA computers during work hours. Abstraction will be limited to determine eligibility only.

Chart will also be reviewed 6 months after the last in-person visit has taken place (and for those lost to follow-up should have taken place). Minimal data will be abstract from the chart -- additional HbA1c, LDLs, and BP measurements from the time of entry into the study to the day of the chart abstraction. Only those with IRB approval will abstract this data and it will only be done on the VA premises. Data written on paper abstraction tools will be entered into the analytic database house behind the VA firewall. Paper documents will be kept on site and in locked filing cabinets in the CMC VAMC Annex.

2. Potential Study Benefits

- 2.1. Assess the potential benefits to be gained by the individual subject, as well as benefits that may accrue to society in general as a result of the planned work.

In our pilot study, poorly controlled diabetics who received mentoring on average improved their HbA1c by 1%. This is a large and clinically significant improvement. If improvements persist then the participant may reduce his or her risk of future complications from diabetes. This study in part will help us understand better if risks persist. This study has the potential also to add to our knowledge about how to better to support diabetics in general with behavioral change.

- 2.2. If the subject does not receive any direct benefit, then it must be stated here and in the consent form.

While we hope that subject will receive benefit it is likely that some participants will not benefit especially those who are randomized to usual care.

3. **Alternate Procedures**

- 3.1 Describe the alternatives available to the subject outside the research context. **N/A**
- 3.2 If none, state that the alternative is not to take part in this research study at all. **The only alternative is to not take part in the research study.**

T. **Data and Safety Monitoring Board (DSMB) or Data Monitoring Committee (DMC) (All Phase III studies are required to have a DSMB. However, the IRB has the right to require a DSMB with any study.)**

- 1. **Will an independent DSMB or DMC oversee the project?** YES NO N/A

- 2.1. If yes, please provide contact information for the DSMB or DMC or Coordinating Center Representative and attach a copy of the charter.

Name: [name] MD

[contact]

Title: DSMB Chair

E-mail: [contact]

- 2. **If a DSMB or DMC will not monitor this study, who will monitor this study? Check all that apply.**

- Principal Investigator
- Sponsor
- VA Cooperative Studies Program
- Safety monitoring committee

U. **Data Monitoring (Monitoring plans describe how a monitor, independent of the study team, regularly inspects study records to ensure the study is adhering to the study protocol and applicable research regulations and CMCVAMC requirements. Monitoring plans do not necessarily require the use of an independent Data and Safety Monitoring Board (DSMB). Such independent boards are usually reserved for high-risk phase I studies, or large, multi-center phase III trials. Federally funded studies may require the use of an independent DSMB.)**

- 1. **Describe the data monitoring plan.** (All protocols must have a data monitoring plan appropriate for the potential risks and the complexity of the study.)

Hypoglycemic events will be monitored at 1, 3 and 6 months. All serious adverse events will be reviewed by the PI and reported to the IRB as well as the DSMB. We do not expect events to differ by arm based on our prior research.

Data not directly entered will be double entered to ensure fidelity. Paper consents will be reviewed routinely for completeness. All files will be regularly maintained and available for inspection upon request.

2. **Describe how protocol deviations, adverse events, serious adverse events, breaches of confidentiality, unanticipated adverse device effect (UADE), and unanticipated or unexpected problems will be reported to the CMCVAMC IRB and sponsor. (Refer to the CMCVAMC IRB Standard Operating Procedure (SOP) Manual for reporting guidelines.) Breaches of confidentiality will reported within 24 hours of our awareness of said breach.**
 - 2.1. Describe the management of information obtain that might be relevant to participant protections such as:
 - 2.1.1. Unanticipated problems involving risks to subjects or others

This is a low risk study. However, if unanticipated problems arise the study team will review them and report them immediately to the CMCVAMC IRB. If there are serious concerns about risks to subjects or others the study will be halted while an external group reviews the study to determine the risks.

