Data Collection: All participants (mentors and mentees) will complete a baseline survey, a short call at 1 and 3 months, a 6 month survey, a 12 month survey, a blood draw at baseline, 6 months, and 12 months and will have their medical health record under electronic review for an additional 6 months after the last in-person visit. Those randomized to arm 2 and further randomized to arm 4 will receive additional short calls at 7 months and 9 months and have one additional in person visit with blood draw at 18 months. A sample of mentors and mentees from stage 1 and stage 2 will be asked to complete qualitative interviews baseline, 6, 12, 18 months. Table 1 identifies data to be collected at each time point and the source of the data.

Table 1: Measurement Schedule							
	Baseline	1 M	3 M	6 M	12 M	18 M	24 M
Dependent Variables							
HbA _{1c} (blood)	x			x	x	x	
Blood Pressure (in person measurement)	x			x	x	x	
Direct LDL (blood)	x			x	x	x	
DM quality of Life (self-report) - Distress	x			x	x	x	
Depression Symptoms (self-report) - Mood	x			x	x	x	
Intervening Variables of Interest							
Social Support	x			x	x	x	
Self-Efficacy (self-report)	x			x	x	x	
Perceived Benefits and Barriers (self-report)	x			x	x	x	
Self-management Behaviors (self-report)	x			x	x	x	
Past Mentoring Dose Received by Current Mentor (Past records)	x						
Mentor's past Change in HbA _{1c} (Past study records)	x						
Mentee's assessment of mentor quality (self-report)				x	x	x	
Potential Confounders							
Demographics (self-report)	x						
Attachment Style (self-report)	x						
Perceived Need for Support (self-report)	x			x	x	x	
BMI (in person measurement)	x			x	x	x	
DM Health History (self-report)	x						
General Health History (self-report)	x			x	x	x	
Potential Contamination (self-report)				x	x	x	
Hypoglycemic Symptoms (self-report)	x	x	x	x	x	x	
Qualitative Perceptions of Program (self-report)	x			x	x	x	
Medical Record Review (Electronic medical record)**						x	x
* Current Mentoring Dose Provided by Mentor will be assessed monthly. For Ease of Presentation we did not include all collection times.							
** Exact timing of EMR review depends on arm – only reviewed once either at 18 or 24 months.							

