2.1. Provide

- 2.1.1. the mode of data collection, e.g. telephone, in-person, questionnaire, interviews,

Data will be collected mostly by in-person survey, interview and lab tests. In addition, mentors will receive short reinforcement calls each month at which time we will collect data about how many times the mentor talked to the mentee in the month. Hypoglycemic symptoms will be assessed by phone at 1 and 3 months (additionally at 7 and 9 months for arms 2 and 4) . Electronic medical records will be reviewed 6 months after the last in person visit. See Table 1 and 2 for details.

- 2.1.2. the precise plan for how data is to be collected or acquired

Surveys will be read to participants and answers will either be directly input into a computer database or written onto paper forms and then transferred to a data base at a later time. The data base will reside on VA servers behind the VA firewall and will never be removed from the server. Paper records will be stored at CHERP behind an electronically locked entrance, a key-locked door and in a key-locked cabinet.

Qualitative interviews will also be read to participants and answers will be voice recorded. Interview data will be stored on the VA server and will be behind VA firewalls This data will be temporarily shared with Alpha Transcription, and University of Pennsylvania's Mixed Methods Research Lab, transcribing and coding respectively. Both companies are approved vendors with appropriate VA approved data security in place.

Data about the number of calls per month made by the mentor will be collected over the phone, and again responses will either be entered directly into a database or first onto paper and then into the database.

Data about hypoglycemic symptoms will be collected over the phone and responses will either be entered directly into a database or first onto paper and then onto the database.

Lab results will be obtained from the lab or via CPRS and entered into the secure research database.

Charts will be abstracted for additional HbA1c, LDL, and blood pressure readings 6 months after the last face-to-face visit.

- 2.1.3. exact location where data will be collected,

CMC VAMC and the CMCVAMC Annex (for in person, phone and chart derived data).

2.1.4. exact location where data entry will take place.

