Testing of Secondary Quantitative Hypotheses:

H4. In those randomized to being a mentee, explore mentor characteristics associated with improved outcomes. Predictors to be evaluated include past mentoring dose of the current mentor, the mentor's past change in HbA_{1c}, the mentor's starting HbA_{1c}, current mentoring dose provided by the mentor, the mentee's evaluation of the mentor, and the mentor's depression score at baseline. Based on the literature and our pilot studies, we have opted to use past mentees as mentors regardless of a. time passed since they were a mentee, b. the amount improvement in HbA_{1c} when they were a mentee, or c. their starting HbA_{1c} in this study. We will evaluate if any of these mentor variables are associated with mentee change in HbA_{1c}, BP, LDL level, DM quality of life score, and depression score at 6 and 12 months and HbA_{1c}, BP, and LDL level at 18 months.

Assessment of Hypoglycemia: In order to assess the relative frequency of minor hypoglycemic symptoms we will summarize the number of participants in each study arm reporting 0, 1-3, or >3 minor hypoglycemic symptoms per month. In order to compare average rates per person per month, using all available data, we will fit a generalized linear mixed model with random subject intercepts and test for differences between treatment groups. Based on our previous study we expect very few major hypoglycemic events, we will compare differences by arm using a Fisher's exact test. If requested by the

Data Safety Monitoring Board (DSMB – see Section E.5 in Human Subjects), preliminary analyses of minor and major hypoglycemic events will be completed before the completion of the study.

Qualitative Analyses:

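### The by-arm comparison of major hypoglycaemia has no planned source for patients who stop responding, or for months 12–18 in arms 1 and 3, although the existing chart review reaches both

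*Combined protocol and SAP*

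**What the plan says.** **Analysis.** Section U.4.2 (Assessment of Hypoglycemia) separates minor symptoms from major events. For the latter it states: "we expect very few major hypoglycemic events, we will compare differences by arm using a Fisher's exact test". It does not define a major event, name its source or set a time window.

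**Source.** Table 1 has one hypoglycaemia row. It is marked as self-report, with entries at baseline and months 1, 3, 6, 12 and 18 and none at month 24. Section M.2.1.1 adds: "Hypoglycemic symptoms will be assessed by phone at 1 and 3 months (additionally at 7 and 9 months for arms 2 and 4"). Section M.1.2 gives the 18-month visit to arms 2 and 4 only.

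**Safety monitoring.** Section U.1 says "Hypoglycemic events will be monitored at 1, 3 and 6 months", which is narrower than Table 1. It also says "All serious adverse events will be reviewed by the PI and reported to the IRB as well as the DSMB".

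**Chart review.** Section M.2.1.2 says "Charts will be abstracted for additional HbA1c, LDL, and blood pressure readings 6 months after the last face-to-face visit". Section S.1.4 gives the same content: "Minimal data will be abstract from the chart -- additional HbA1c, LDLs, and BP measurements". It runs from study entry to the day of abstraction and includes patients lost to follow-up, timed from when their last visit was due. The footnote to Table 1 says that each record is reviewed once, at 18 or 24 months by arm. The survival-data item in section R.3 is marked N/A.

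**Efficacy in the same period.** Under H2 in section U.4.2, the 18-month tests of HbA1c, blood pressure and LDL use values from the electronic record.

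**The concern.** A self-report item captures only what a patient is still there to report. Someone who is admitted, dies or stops answering after a severe episode drops out of the count, and loss may be related to the event. The trial is open, and contact frequency differs by arm. With very few events expected, one or two uncaptured cases could change the comparison.

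The chart is the one source read in the same way in every arm, and it covers patients who are lost. As written, it extends the follow-up of benefit but adds nothing on harm. At stake is whether a claim of sustained HbA1c improvement at 18 months can be set beside hypoglycaemia data for the same months.

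**Working it through.** **1. The plan's own figures.** The plan has no power figure or expected rate for hypoglycaemia. Its only sample-size calculation is for HbA1c (section U.4.1: difference 0.8, SD 1.6, 80% power). With the two-sided 5% level stated under H2, n = 2 × (1.960 + 0.842)² × (1.6/0.8)² = 62.8, so 63 per arm; the t-based version gives 63.8, so 64. With 10% attrition, 64/0.90 = 71.1, so 72. Both stated figures reproduce, but neither bears on hypoglycaemia.

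**2. Coverage by arm.** The inputs are Table 1, sections M.1.2 and M.2.1.1, and the 18-month efficacy tests in section U.4.2.

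| | Arms 1 and 3 | Arms 2 and 4 |
|---|---|---|
| Post-baseline hypoglycaemia contacts (months) | 1, 3, 6, 12 (four) | 1, 3, 6, 7, 9, 12, 18 (seven) |
| Last contact | 12 | 18 |
| Chart review | 12 + 6 = 18 | 18 + 6 = 24 |
| Months in chart window with no hypoglycaemia question | 18 − 12 = 6; 6/18 = 33% | 24 − 18 = 6; 6/24 = 25% |
| Last efficacy test | 18 | 18 |
| Efficacy follow-up beyond last hypoglycaemia contact | 18 − 12 = 6 months | 18 − 18 = 0 months |

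The last row is the relevant one. Efficacy outruns hypoglycaemia ascertainment only in arms 1 and 3, in months 12–18.

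**3. Patients who stop responding.** For them the calls and visits yield nothing after the last contact. The chart review still reaches them, but sections M.2.1.2 and S.1.4 both list only HbA1c, LDL and blood pressure. No section adds hypoglycaemia, emergency visits, admissions or death to the abstraction. Section U.1 says that serious adverse events are reviewed and reported, but not how one is found in a patient with whom there is no contact.

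**4. Unequal exposure in the planned test.** Fisher's test counts patients with an event and ignores time at risk. For rare events at the same constant rate in every arm, self-report over 18 against 12 months gives arms 2 and 4 about 18/12 = 1.50 times the events. Chart data over 24 against 18 months would give 24/18 = 1.33 times. Adding chart events without a common window would therefore leave an exposure imbalance.

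**5. What cannot be computed.** Bias in the comparison would need the event rate, the loss in each arm, and the event risk in those lost relative to those retained. The documents give none of these.

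**The case against.** The strongest reply is that the abstraction is minimal by design. Section S.1.4 asks how confidentiality risk will be limited, section S.1.2 calls loss of confidentiality the greatest risk, and the study is rated minimal risk. Mentoring lasts 6 months and is covered by contacts at months 1, 3 and 6. The uncovered window in arms 1 and 3 starts 6 months after mentoring ends, and arm 1 receives none. All of this stands, and it is why the point is an improvement rather than a serious fault. It does not explain how a stated by-arm safety comparison is to handle patients who stop responding.

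A reader might infer more than the documents support:

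- *That section U.4.1 implies 171 − 144 = 27 mentees lost, and so a computable share of missed events.* The margin is an allowance, not a forecast. Section M.1.1 says that over-enrolment also covers removing people unsuited to mentoring, who are not thereby lost. Those who do leave may already have answered early calls. Section K.3.1 gives 206 stage 1 mentees, not 171. Any percentage would also need invented event risks.
- *That efficacy outruns safety in every arm.* No efficacy test is planned at 24 months, and arms 2 and 4 have a hypoglycaemia question at their 18-month visit.
- *That events are certain to be missed, or that DSMB reports cover attenders only.* Section U.1 covers all serious adverse events without that limit, and the DSMB charter and IRB procedures are not in the documents.
- *That the N/A in section R.3 exempts deaths from reporting.* It answers only whether survival data are required.

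Self-report as the source of major events is itself an inference: it is the only hypoglycaemia source on the schedule, but section U.4.2 names none.

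**Conclusion.** The point holds as a gap in planned ascertainment. There is no stated means of capturing major hypoglycaemic events in patients who stop responding, or in months 12–18 of arms 1 and 3 (6 of 18 months), the window that ends in the record-based 18-month efficacy test. Contact is also unequal: seven post-baseline contacts in arms 2 and 4 against four in arms 1 and 3.

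This rests on reading Table 1's self-report row as the source of major events, and on the two matching lists of chart items being complete. Neither the direction nor the size of any bias can be derived, so the documents do not support a conclusion that the safety result would be falsely reassuring. The change is worth making because it is cheap and uses a review already planned for all enrolled participants.

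**What to change.** 1. **Sections M.2.1.2 and S.1.4.** Add to the chart abstraction VA emergency visits or admissions for hypoglycaemia, with dates, and date of death. Apply this to all enrolled participants, including those lost, subject to what is permitted after formal withdrawal, which section R.2 does not address. Amend section R.3 to match. Other admissions are not needed.
2. **Section U.4.2.** Name the sources for major events. Compare arms on self-report and chart events combined, labelled by source, over a window common to the arms compared. Examples are randomisation to month 18 for mentoring against usual care, and months 6 to 24 for former mentees who do and do not become mentors. Show chart-only events as well, because that source is the same in every arm.
3. **Section U.1.** Reconcile the monitoring months with Table 1 and section M.2.1.1.

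**Cost.** A few more minutes on a review that Table 2 already puts at 15 minutes per participant, and an amendment to the IRB and HIPAA data lists. No visit, procedure or staff is added. Care outside the VA would still be unseen. A single review at 18 or 24 months cannot give the DSMB timely reports, so the serious adverse event route in section U.1 stays necessary.
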